Secondary Objectives	To evaluate the effect of acupressure and standardized curcuminoid from turmeric extract vs placebo at 3 weeks : 
 • Knee pain as measured by the VAS score • Joint stiffness and joint functional ability are assessed by the WOMAC score • The independence of the elderly as assessed by the Barthel Index • Quality of Life were measured by Respondents' satisfaction in carrying out daily activities based on indicators on the KOOS instrument
Study design	Randomized controlled trial, double-blind to assess efficacy, tolerability and safety combination of acupressure and curcuminoid versus placebo. Patients can be pre-screened for certain x-ray and laboratory parameters. Following a screening visit, eligible subjects will enter the wash-out for 1 week. After the wash-out period, eligible subjects will be randomized and treated for 3 weeks. The total duration of the study is up to 5 weeks
Population	Approximately 70 female and male patients ≥ 65 years old
Key Inclusion criteria	
 • Clinical diagnosis of osteoarthritis which confirmed by physical examination and x-rays • Experience pain with a Numeric Rating scale of 1-7 • Must be able to swallow capsules • Must be able to carry out mobility without assistance or with minimal assistance

Key Exclusion criteria	
 ● Parkinson's disease ● Dementia disease ● Psychosis disease ● New bone fractures ● Joint dislocations ● Cancer ● Rheumatic diseases other than osteoarthritis (rheumatoid arthritis) ● Undergoing joint replacement therapy. ● Analgesic dependent disease
Study treatment	
 ● Combination of Acupressure and Curcuminoid from turmeric extract ● Placebo
Efficacy assessments	
 ● Leukocytes ● Neutrophil Leukocyte Ratio ● Blood Sedimentation Rate ● Pain ● Secretion of COX-2 in blood ● Secretion of Endorphin hormones in blood
Key safety assessment	
 ● Physical examination ● Vital signs ● Monitoring of laboratory markers in blood
Others assessment	
 ● Quality of Life

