3.1 Study design

Randomized controlled trial, we will conduct a 2-arm, double-blind (patient and investigational blinded) to assess efficacy, tolerability and safety combination of acupressure and curcuminoid versus placebo.

Pre-Screening:

Patients can be pre-screened for certain x-ray and laboratory parameters. Following a screening visit, eligible subjects will enter the wash-out. After the wash-out period, eligible subjects will be randomized and treated for 3 weeks. The total duration of the study is up to 5 weeks.

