3.2 Study setting and source population

Eligible participants were individuals recruited from communities covered by government-owned primary care hospitals who consulted a rheumatology subspecialist physician with symptoms of pain and discomfort around the knee.

Participants will be recruited from August 2023 to September 2023. An informed-consent form will be provided to participants in their local language to gain credibility. Codes will be assigned to ensure confidentiality for data collection, with only the primary researcher having access to the participant codes for each group. Participants providing their consent will be further screened for eligibility.

4 Population

The study population will consist of male and female patients (≥ 65 years old) with Osteoarthritis (Osteoarthritis with knee joint pain, knee joint stiffness in the morning less than 30 minutes, Crepitus, deformity, joint swelling (right and left asymmetrical), Other signs of inflammation (a feeling of even warmth and reddish color). The goal is to randomize a total of approximately 70 patients. Since a 25% screening failure rate and a 20% washout failure rate is expected, approximately 100 patients will be screened.

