4.3 Eligibility test procedure

Radiographs will be used to assess participants for Osteoarthritis using the Kellgren and Lawrence criteria which divide Osteoarthritis from mild to severe. It should be remembered that at the beginning of the disease, the radiographic appearance of the joint still looks normal. According to Kellgren and Lawrence, radiologically, osteoarthritis is classified as follows:

- 1) Grade 0: Normal, no signs of osteoarthritis
- 2) Grade 1: Doubtful, without osteophytes, doubtful joint narrowing

3) Grade 2: Minimal, few osteophytes on the tibia and patella and the joint surface is asymmetrically narrowed.

4) Grade 3: Moderate, there are moderate osteophytes in several places, the joint surface is narrowed, and subchondral sclerosis appears.

5) Grade 4: Severe, presence of large osteophytes, complete narrowing of the joint surface, severe subchondral sclerosis, and joint surface damage.

Mini Mental State Examination (MMSE) test will be used to assess the patient's cognitive abilities. This is important to ensure that patients can understand the instructions in the treatment process and the outcome measurement process.

5 Randomization, allocation and blinding

A total of 70 eligible participants will be randomized to the group with curcuminoids capsules and acupressure (C+A; group 1) or the group with placebo and sham acupressure (P+S; group 2) via lottery randomization. Thereafter subjects will be randomly allocated to C+A and P+S group. The schematic CONSORT (Consolidated Standards of Reporting Trials) flow diagram for the study protocol is presented in Figure 1. Schematic CONSORT (Consolidated Standards of Reporting Trials) flowchart for the study.

[figure not shown]

Figure 1. Schematic CONSORT (Consolidated Standards of Reporting Trials) flowchart for the study

Determination of baseline characteristics for every participant will be done by the therapist through a standardized assessment form. During the baseline measurement, the following characteristics will be recorded: sex, age, body mass, pain characteristic, history of disease and medication use. The participant's participation schedule will be determined according to the SPIRIT (Standard Protocol Items: Recommendations for Interventional Trials) statement Figure 2. The primary and secondary outcome measures will be recorded before providing the intervention.

[figure not shown]
TIMEPOINT**	STUDY PERIOD								
	Enrolment	Allocation	Post-allocation			Close-out			

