KOOS is an instrument to assess patient opinions about the condition of the knee and problems related to the knee. KOOS has been translated into Indonesian and tested for validity by Phatama (Phatama & et al, 2021) with Cronbach α results of 0.84 to 0.97 for all subscales, indicating adequate internal consistency. Test-retest reliability was excellent, with intraclass correlation coefficients ranging from 0.91 to 0.99 for all subscales. No significant differences were found in KOOS subscale responses between the first administration of the questionnaire and the second administration within 21 days. The Indonesian version of the KOOS was declared valid and reliable and therefore is an objective instrument for evaluating knee ligament injuries and knee osteoarthritis in the Indonesian population. KOOS can be used as a measurement of quality of life because it includes measurements of 5 subscales, namely (1) Symptoms; (2) Rigidity; (3) Pain; (4) Daily Activities; (4) Sports and Recreation Activities and (5) Knee-related Quality of Life. in circumstances one week prior is the time period considered when answering the question. Answer options are standard (Likert scale) and each question is scored from 0 to 4. Scores are normalized (a score of 100 indicates no symptoms and 0 indicates extreme symptoms).

8 Statistical Issues

Sample size

Sample size is estimated by the following formula

$$N = \frac{2\sigma^2(Z_{1-\alpha/2} + Z_{1-\beta})^2}{(\mu_1 - \mu_2)^2}$$

where N is the sample size required in both groups, σ is the standard deviation of the primary outcome. This research has a confidence level (1 - α) of 95%, so the value obtained is $\alpha = 5\%$. Therefore, the research hypothesis is unidirectional, so the magnitude of $Z_{1-\alpha} = 1.96$. Power (1 - β) in the research was also set at 80%, so that the value of $\beta = 20\%$ then the amount of $Z_{1-\beta} = 0.842$. Previous research analyzed changes in leukocytes in subjects treated with curcuminoid therapy from turmeric extract 30 mg 3 times a day for 14 days, amounting to 30.00 ± 5.10 and meloxicam 1 x 15 mg per day, obtained the mean delta value of leukocytes in the control group was $164.1+50.91$ and the treatment group was $174.27+78.93$.

$$N = \frac{2\sigma^2(Z_{1-\alpha/2} + Z_{1-\beta})^2}{(\mu_1 - \mu_2)^2}$$

$$= \frac{2(14,01)^2(1,96+0,842)^2}{(174,27-164,1)^2}$$

$$N = \frac{392,5602 (2,802)^2}{(174,27-164,1)^2}$$

$$N = \frac{3082,07}{103,4289}$$

$$N = 29,79 - (30 \text{ orang})$$

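### At the plan's own failure rates, 100 screened gives about 60 to randomise, not 70 (70 needs about 117), and section 8's 36 per group does not match the 70 used elsewhere

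*Combined protocol and SAP*

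**What the plan says.** Section 4 (Population) sets the target, "The goal is to randomize a total of approximately 70 patients", and the screening forecast, "Since a 25% screening failure rate and a 20% washout failure rate is expected, approximately 100 patients will be screened". The protocol summary also gives the size as "Approximately 70 female and male patients". Section 5 drops the qualifier: "A total of 70 eligible participants will be randomized".

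The order of the stages is clear. The summary says "Following a screening visit, eligible subjects will enter the wash-out for 1 week", and section 3.1 says "After the wash-out period, eligible subjects will be randomized and treated for 3 weeks". Patients are therefore lost at screening, then at wash-out, and only those who remain are randomised.

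Section 8 (Sample size) computes N = 30 from a two-means formula, described as "where N is the sample size required in both groups". After the calculation it calls this figure the total for the two groups. In the next sentence it allows for 20% dropout and arrives at 36 in each group.

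**The concern.** The forecast of 100 is presented as following from the two failure rates, and it does not. Reaching 70 from 100 allows a combined loss of 30%. Rates of 25% and 20% give 40% when applied in sequence and 45% when added. Recruitment effort is therefore understated, and section 3.2 sets a short window: "Participants will be recruited from August 2023 to September 2023".

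The randomised total is also not derived consistently. Section 8 leads to 72, and section 5 randomises 70. Neither is expected to keep 30 evaluable patients per group after the dropout that section 8 itself assumes, yet 80% power is stated on the basis of 30. At stake are a realistic recruitment forecast and a power statement that matches the number randomised.

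**Working it through.** **Screening (section 4)**

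Inputs: target about 70; screening failure 25%; wash-out failure 20%; about 100 screened (all section 4). Both losses precede randomisation (summary, section 3.1).

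Expected randomised = screened × (1 − 0.25) × (1 − 0.20).

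- Sequential losses: 100 × 0.75 × 0.80 = 60. That is 10 below 70, or 10/70 = 14%.
- Both rates as shares of all screened: 100 × (1 − 0.25 − 0.20) = 55.
- Expected screenings for 70: 70/0.60 = 116.7, so 117. With added rates: 70/0.55 = 127.3, so 128.
- Understatement on the sequential reading: 117 − 100 = 17.

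Attempts to reproduce 100:

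- Screening loss alone gives 70/0.75 = 93.3, and wash-out loss alone gives 70/0.80 = 87.5. Each ignores a stated loss.
- Marking up by the sum of the rates gives 70 × 1.45 = 101.5. This is close to 100 but is not a valid calculation.
- 100 is exactly the expected number for 60 randomised (60/0.60).

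The documents do not say how 100 was reached.

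To see whether chance could cover the gap, treat each screened patient as independently reaching randomisation with probability 0.60 (an assumption). The binomial chance of at least 70 is about 2.5% from 100 screened and about 55% from 117. So 117 is an expected value, not a guarantee.

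**Sample size (section 8)**

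Inputs: σ = 14.01; difference 174.27 − 164.1 = 10.17; Z values 1.96 and 0.842; dropout 20%.

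- Plan's own figure: N = 2 × 14.01² × (1.96 + 0.842)² / 10.17² = 3082.07/103.4289 = 29.80, rounded up to 30. It reproduces. This formula gives the number **per group**.
- Plan's dropout allowance: 30 × 1.2 = 36. It reproduces, but multiplying by 1.2 does not offset a 20% loss. The allowance that does is 30/(1 − 0.20) = 37.5, so 38.

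| Per group | Total | Evaluable per group after 20% dropout | Dropout that still leaves 30 | Expected screenings (total/0.60) |
|---|---|---|---|---|
| 35 (section 5's 70, split equally) | 70 | 35 × 0.8 = 28 | 1 − 30/35 = 14.3% | 117 |
| 36 (section 8) | 72 | 36 × 0.8 = 28.8 | 1 − 30/36 = 16.7% | 120 |
| 38 (30/0.8, rounded up) | 76 | 38 × 0.8 = 30.4 | 1 − 30/38 = 21.1% | 127 |

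No reading of section 8 gives 70. It gives 30 by its own label, 72 as stated, or 76 with the dropout allowance done by division.

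**The case against.** The strongest reply is that none of this touches the validity of the trial. The target is what the plan commits to, 100 is a forecast, and nothing caps screening. The investigators can go on screening until they have 70. That is right. It would be wrong to treat 60 as the number randomised and compute a loss of power from it. The objection limits the weight of the point but does not rescue the arithmetic: the plan derives 100 from the two rates, and the word approximately does not stretch from 60 to 70.

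The section 8 points are also open to challenge as very small, and they are.

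- The label on N = 30 misleads nobody, because the next sentence uses it as per group.
- A total of 72 fits the approximate 70 in the summary and section 4. Only section 5 states 70 without a qualifier.
- On the plan's own inputs (normal approximation, two-sided 5%), power is 80.3% with 30 evaluable per group, 78.7% with 28.8 and 77.5% with 28. The loss is about 2 to 3 percentage points.

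Finally, those power figures depend on σ = 14.01, which equals half the difference between the two quoted standard deviations, (78.93 − 50.91)/2, and is not a pooled value. That is a separate and larger question, and settling it may replace the section 8 numbers altogether. It is a reason not to write new power figures into the protocol now. It has no bearing on the screening arithmetic.

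**Conclusion.** The concern holds and is minor. On the plan's own rates, 100 screened yields about 60 to randomise (55 if the rates are added) against a target of about 70, and the expected number of screenings for 70 is 117. This rests only on the two stated rates and the stated order of the stages. The likely consequence is about 17 more screenings or a longer recruitment period. The documents give no site throughput, so the effect on the August to September 2023 window cannot be measured.

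In section 8, 36 or 35 per group is expected to leave 28.8 or 28 evaluable against the 30 behind the stated 80% power, a gap of 1 to 2 patients per group. The totals of 72 and 70 differ by 2. The CONSORT figure in section 5 is not visible in the text available, so any numbers in it could not be compared.

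**What to change.** 1. **Section 4:** change the forecast from about 100 to about 117 and call it an expected value (70/0.60). If 100 is right, restate the failure rates so that they combine to a 30% loss.
2. **Section 8:** label N = 30 as per group, both where N is defined and in the sentence after the calculation.
3. **Summary and sections 4, 5 and 8:** state one per-group size and one matching total. Which size to keep is the sponsor's choice, and the screening forecast follows from it: 117 for 70, 120 for 72, 127 for 76.
4. **If 70 is kept:** say that about 28 per group are expected to be evaluable after 20% dropout, fewer than the 30 on which 80% power was calculated, and do not claim 80% after dropout. A choice of 72 needs the same caveat, with 28.8. Do not insert a replacement power figure until σ is settled.

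These are text changes. Under section 11.1 they need a written amendment approved by the IRB/IEC, and by health authorities where required, and they can go into any other amendment. The 17 additional screenings are already implied by the plan's own rates. Keeping 70 adds no randomised patients and gives up the post-dropout claim of 80% power; 72 adds 2 and 76 adds 6.

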4.1 Inclusion criteria

Patients eligible for inclusion in this study must fulfill all of the following criteria:

1. Clinical diagnosis of osteoarthritis which confirmed by physical examination and x-rays
2. Experience pain with a Numeric Rating scale of 1-7
3. Must be able to swallow capsules
4. Must be able to carry out mobility without assistance or with minimal assistance

4.2 Exclusion criteria

Patients fulfilling any of the following criteria are not eligible for inclusion in this study. No additional exclusions may be applied by the investigator, in order to ensure that the study population will be representative of all eligible patients.

1. Parkinson's disease
2. Dementia disease
3. Psychosis disease
4. New bone fractures
5. Joint dislocations
6. Cancer
7. Rheumatic diseases other than osteoarthritis (rheumatoid arthritis)
8. Undergoing joint replacement therapy.
9. Analgesic dependent disease

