2.1 Primary objective

To determine the effectiveness of combination two regimens (acupressure and curcuminoid) as measured by changes from baseline (BL) in Leukocytes, Neutrophil Leukocyte Ratio, Blood Sedimentation Rate, Pain, secretion of COX-2 and Endorphin hormones in blood to placebo after 3 weeks of treatment in elderly patients with Osteoarthritis

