		0	1 st week	2 nd week	3 rd week	1 st day	1 st week	2 nd week	Post 3 rd week
ENROLMENT:									
Eligibility screen	X								
Informed consent	X								
[Radiography and MMSE Test]	X								
Allocation		X							
INTERVENTIONS:									
[C+A Therapy]			X	X	X				
[P+S Therapy]			X	X	X				
ASSESSMENTS:									
[Demographic Details]	X								
[Inflammatory Marker]						X			X
[Endorphine]						X			X
[Quality of Life]						X	X	X	X

Figure 2. SPIRIT (Standard Protocol Items: Recommendations for Interventional Trials) recommended schedule for participation.

6 Intervention

After the standardized assessments and baseline measurements, the intervention will be conducted. Participants will be randomly assigned to the CA group or the PS group. For Acupressure Therapy and Sham Acupressure, each participant will be exposed to 3 therapy sessions per week of 20 minutes for 3 consecutive weeks. Participants will not be allowed to take any medication routinely during this time except for antihypertensive agents, thyroid medications, and antidiabetic drugs. To help participants adhere to the interventions, reminder messages will be sent before each session visit. For Curcuminoid capsules and placebo, Each participant will be exposed to taking capsules three times a day for 21 days.

Acupressure to perform CA, the patient is put in the supine position with legs straight. Prepare tools and materials such as a seat (or bed), warm water, olive oil, wet & dry tissue, towels. The therapist washes his hands, the client sits in a comfortable position. Teach patients breathing relaxation techniques to use during therapy. Give patients the opportunity to pray according to their respective beliefs. Make sure the client is relaxed and comfortable. Help remove the client's clothing or accessories that may hinder the acupressure action being performed, if necessary. Perform a client pain assessment. Wipe the client on the parts to be massaged with warm water that has been treated with a disinfectant solution using a small towel. Dry with a clean towel. Use cream or oil, do a warming massage with basic massage techniques, choose according to the client's condition (rubbing, squeezing, pressing) and stretching the patient's feet. Acupressure massage points are performed at ST34, ST36, Tai Xi Acupoint, GB34, SP 9, SP 8, EX-LE, EX-LE3, EX-LE4, EX-LE6, EX-LE7, EX-LE10

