The patient is observed for a local twitch response. The patient is asked to report any abnormal sensations or discomfort during the course of intervention.

The sponsor will provide double-blind study medication for Curcuminoid and Placebo

Preparation of standardized curcuminoid turmeric extract preparations. Samples were made from extracted turmeric and then optimized. The capsule formulation is made from turmeric rhizome extract which contains 30 mg of curcuminoids per capsule. In the study, standardized curcuminoid turmeric extract was given in capsules at a concentration of 30 mg 3 times a day for 3 weeks.

7 Outcomes

All outcome measures will be assessed at baseline and after 3 weeks of intervention.

Primary Outcomes measures

1) Inflammatory Markers

Inflammation markers are carried out by measuring leukocyte numbers and the Neutrophil Lymphocyte Ratio. The examination is carried out using a complete blood test using a Hematology Analyzer, which is a laboratory tool used to measure and count the number of blood cells. The blood samples are mixed using a mixture of reagents to create a process called hemolyzing. This process will be divided into several purposes, to measure leukocytes, neutrophils, platelets and erythrocytes.

2) Secretion of the COX-2 hormone

The enzyme cyclooxygenase-2 (COX-2) is an important mediator in increasing the inflammatory response. In the blood plasma of patients with osteoarthritis, the COX-2 enzyme can be detected. The COX-2 hormone examination was carried out using the Enzyme Linked Immunosorbent Assay (ELISA) method on blood plasma.

3) Secretion of endorphin hormones

Endorphins, in this case beta endorphin, are hormones released by the pituitary gland in response to stress or pain, which are also secreted in blood plasma. Endorphin hormone levels in the blood were measured before starting therapy and after 3 weeks of therapy.

Endorphin hormone examination is carried out using the Enzyme Linked Immunosorbent Assay (ELISA) method on blood plasma that has been incubated at room temperature for 10-20 minutes, then the tube will be centrifuged for 20 minutes at a speed of 2000-3000 rpm.

Secondary outcomes

The effectiveness of therapy is the ability of the therapy regimen given to suppress several other expected output indicators. Other output indicators were measured before starting therapy and after 3 weeks of therapy

1) Knee pain as measured by the VAS score

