9.2 Adverse events

We will look for the presence of any adverse events that might occur during each administration of CA Therapy, which include increased soreness, pain, numbness, and tingling. Any adverse event that is life-threatening or related to significant disability will be reported to the ethics research committee of the institution.

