10.4 Publication of study protocol and results

The key design elements of this protocol will be posted in a publicly accessible database such as clinicaltrials.gov. In addition, upon study completion and finalization of the study report the results of this trial will be either submitted for publication and/or posted in a publicly accessible database of clinical trial results.

11. Protocol adherence

This protocol defines the study objectives, the study procedures and the data to be collected on study participants. Additional assessments required to ensure safety of patients should be administered as deemed necessary on a case by case basis. Under no circumstances is an investigator allowed to collect additional data or conduct any additional procedures for any research related purpose involving any investigational drugs under the protocol.

Investigators ascertain they will apply due diligence to avoid protocol deviations. If an investigator feels a protocol deviation would improve the conduct of the study this must be considered a protocol amendment, and unless such an amendment is agreed upon by the IRB/IEC and health authorities, where required, it cannot be implemented.

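### Acute infection is neither excluded nor flagged at the two blood draws, so the primary blood markers carry avoidable noise and lose power

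*Combined protocol and SAP*

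**What the plan says.** Section 7, under the primary outcome measures, puts two blood-count markers first: "Inflammation markers are carried out by measuring leukocyte numbers and the Neutrophil Lymphocyte Ratio". The primary objective in Section 2.1 is wider: "Leukocytes, Neutrophil Leukocyte Ratio, Blood Sedimentation Rate, Pain, secretion of COX-2 and Endorphin hormones in blood". Section 7 and the schedule in Figure 2 give each blood marker two time points, one before treatment and one after week 3.

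Section 4.2 lists nine exclusions. The nearest to an inflammatory confounder is "Rheumatic diseases other than osteoarthritis (rheumatoid arthritis"). None is infection, fever or acute inflammatory illness, and no inclusion criterion in Section 4.1 requires their absence. Section 4.2 also says: "No additional exclusions may be applied by the investigator, in order to ensure that the study population will be representative of all eligible patients".

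Five other places touch on the matter without settling it:

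- Section 3.1: "Patients can be pre-screened for certain x-ray and laboratory parameters". This is optional and gives no parameter or cut-off.
- Section 5: disease history and medication use are recorded at baseline.
- Section 6: "Participants will not be allowed to take any medication routinely during this time except for antihypertensive agents, thyroid medications, and antidiabetic drugs". This restricts medicines and does not mention infection.
- Protocol summary: physical examination, vital signs and laboratory monitoring are key safety assessments.
- Section 9.2: adverse events are looked for at each session of the active therapy, "which include increased soreness, pain, numbness, and tingling".

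Section 9.3 provides for a Shapiro-Wilk test, then t or Mann-Whitney tests between groups and paired t or Wilcoxon signed-rank tests within groups. It has no covariate, no sensitivity analysis and no rule for a sample taken during an illness.

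**The concern.** Leukocyte count and the neutrophil ratio are systemic markers. They move with any acute infection, whatever happens in the knee. With one sample before and one after, an infection at either draw goes whole into that participant's change score, and no repeat sample dilutes it. The list removes cancer, new fractures and other rheumatic disease, so acute infection stands out as a gap. Because the site may not add exclusions, Section 4.2 gives it no stated basis for turning away an infected patient who meets the criteria.

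Two things are at stake. One is the precision of the between-arm comparison, in a trial sized with little margin. The other is the reading of the within-group tests, where an arm that happens to include several people recovering from a baseline infection would appear to improve.

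**Working it through.** **1. The plan's own sample size.** Section 8 uses a difference of 174.27 − 164.1 = 10.17, SD 14.01, and z values 1.96 and 0.842:

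N = 2 × 14.01² × 2.802² / 10.17² = 3082.07 / 103.43 = 29.80, so 30 per group.

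The plan prints 29.79 and rounds to 30, so the figure reproduces. It makes no allowance for infection. Sections 4 and 5 randomise 70; I assume equal arms of 35, since no ratio is stated.

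**2. Assumed inputs, none of them in the documents.**

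- SD of leukocyte change without infection: 1.5 ×10^9/L.
- Probability q of infection at any one draw: 1%, 2% or 5%, equal in both arms and at both draws.
- Shift S caused by infection: 6 or 3 ×10^9/L.
- Treatment difference set to give about 80% power at 35 per arm without infection: 2.802 × 1.5 × √(2/35) ≈ 1.0 ×10^9/L.

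**3. Variance of the change score.** Var = 1.5² + 2q(1 − q)S². For q = 1% and S = 6: 2.25 + 2 × 0.01 × 0.99 × 36 = 2.963, so the SD is 1.72. The information left for a comparison of means is 2.25 / 2.963 = 76%.

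**4. Power under the plan's rule.** The last column is simulated: t test if Shapiro-Wilk does not reject, Mann-Whitney if it rejects in either arm. Section 9.3 does not say how the normality test is applied, so that reading is also an assumption.

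| S (×10^9/L) | q per draw | SD of change | Information, means | Power, plan's rule |
|---|---|---|---|---|
| none | 0 | 1.50 | 100% | about 80% |
| 6 | 1% | 1.72 | 76% | 73% |
| 6 | 2% | 1.91 | 61% | 68% |
| 6 | 5% | 2.38 | 40% | 59% |
| 3 | 1% | 1.56 | 93% | 76% |
| 3 | 2% | 1.61 | 86% | 73% |
| 3 | 5% | 1.76 | 72% | 66% |

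Repeat simulations differ from these powers by up to about three percentage points. With S = 6, Shapiro-Wilk rejected in at least one arm in 53%, 71% and 88% of simulated trials, so the rank test is often used. The t test alone would have had 67%, 59% and 43% power.

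**5. False positives.** With no treatment effect and S = 6, the type I error stayed at about 4% to 5% at all three rates. One affected draw moves an arm mean by 6/35 = 0.17 ×10^9/L, or 0.17/1.5 = 0.11 SD.

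**6. What an entry exclusion alone would recover.** On the plan's own scale (difference 10.17, SD 14.01, 30 analysed per arm), simulated Mann-Whitney power is about 77% without infection. If 5% of draws are infected and each shifts the change by 3 SD, it is 60% with infection possible at both draws and 69% with infection possible only at follow-up. At 2% and 2 SD the figures are 72% and 74%. Screening at entry therefore recovers only part of the loss; infection arising during the 3 weeks must be handled separately.

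**The case against.** Several stronger readings are tempting, and the documents do not support them.

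- **That Section 11 stops infection being recorded.** It does say "Under no circumstances is an investigator allowed to collect additional data", but the sentence goes on to limit this to research purposes, and the sentence just before it allows additional safety assessments case by case. Section 9.2 looks for any adverse events and its list is illustrative. With three sessions a week, vital signs and physical examination, an illness has several places to surface. What is missing is a specific infection item at the draw and a rule for using it. Section 9.2 names only the active therapy, so capture in the control arm is less clear.
- **That an infected patient has to be enrolled and sampled.** No section requires blood to be drawn on a day of acute illness, and the pre-screen and one-week wash-out leave some room. Neither defines infection or a limit, so this is only partial protection.
- **That illness in week 3 counts as a treatment failure.** The plan has no responder or failure classification; it compares groups on measured values.
- **That infection biases the arm comparison.** Randomisation makes baseline infection independent of arm, and nothing in the documents suggests that treatment alters infection risk. Chance imbalance is already covered by the test's error rate, as step 5 shows.
- **That infection will overwhelm the signal.** With the smaller shift at 1% or 2% of draws the loss is modest. The information figures of 76%, 61% and 40% apply to a comparison of means and overstate the loss under a rule that often moves to a rank test.

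The within-group concern also has a limit. If infection is equally common at both draws, its average effect on an arm's change is zero. It misleads when baseline infections happen to outnumber those at follow-up.

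**Conclusion.** The gap is real. Two primary markers that respond to infection are each measured only twice, infection is absent from a closed exclusion list, and no other section links it to eligibility, draw timing or analysis. The harm between arms is lost power: from about 80% to between 76% and 59% over the assumed range. The size depends on the assumed infection rate, shift and SD, since the documents give no infection rate or marker shift.

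The illustration covers leukocyte count only. Sedimentation rate may be exposed in the same way, but it appears in the primary objective and not among Section 7's primary outcomes; COX-2 and endorphin were not examined. The illustration also takes the plan's 80% power as its starting point. Whether the SD of 14.01 supports that is a separate question: it equals half the difference between the two source SDs, (78.93 − 50.91)/2.

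This is a worthwhile, inexpensive improvement and not a flaw that invalidates the comparison.

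**What to change.** 1. In Section 4.2, add an exclusion for acute infection, fever or acute inflammatory illness at the baseline draw, or allow the draw and randomisation to be deferred until it has resolved. State how this fits the one-week wash-out and the 5-week total: 5 − 1 − 3 leaves one week for screening and any deferral.
2. Add a yes/no item on current or recent infection to the data form at both draws, in both arms, with the look-back period defined.
3. In Section 9.3, prespecify a sensitivity analysis of the blood markers that leaves out draws taken during infection. Keep the analysis of all randomised participants as the main one, because infection after randomisation is a post-randomisation event and dropping those participants gives up the protection of randomisation.

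The cost is one eligibility line, one form item and one extra table, plus a few deferred or excluded patients and a slightly narrower population. Without the form item, affected draws may be impossible to identify afterwards.
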